Participants will then be randomized to one of two groups: 1) to receiving weekly educational text or email messages about the positive health effects of maintaining a normal body mass index, particularly as it relates to MS, or 2) standard of care (no additional contact). At the routinely-scheduled infusions at months 3 and 6, body mass index, waist circumference, and fatigue/HRQoL/self-esteem will be evaluated. Serum and plasma will be collected for future studies.

Enrollment and Randomization: In order to maximize enrollment within the period of support, people with MS who receive monthly natalizumab infusions and meet other criteria (see #3 inclusion/exclusion criteria) will be offered participation in the study. Potential participants may be notified when receiving their regularly scheduled appointment reminder phone call that a study team member may approach them during their upcoming infusion visit about enrollment in the study. The Johns Hopkins MS Center infusion center currently provides natalizumab infusions for

Date: 7/20/16

Principal Investigator: [name], MCR

Application Number: IRB00095554

140 MS patients per month; it is estimated that two-thirds have a body mass index ≥ 25 kg/m². Participants will be randomized by the study statistician 1:1 to the frequent patient activation arm or standard of care.

Study Procedures/Schedule of Events:

Patients will be consented one month prior to the baseline visit so they can be given adequate notice and can be given a stool sample collection kit to bring it at their next infusion. At the consent visit, baseline energy requirement will be determined (see below) and the patient's waist circumference will be measured. Waist circumference will be measured according to NIH protocol (patient standing with feet shoulder width apart, arms crossed over chest, and abdominal muscles relaxed, with measurement taken at the top of the iliac crest, at the end of normal expiration).

At the baseline visit, the following will be done:

- Vital signs and waist circumference
 - i. If waist circumference varies $\geq 10\%$ from the consent visit, baseline energy requirement will be re-calculated
- Patient-Determined Disease Steps

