- Health-related quality of life, (Functional Assessment in MS [FAMS]), fatigue (PROMIS fatigue), Pittsburgh Sleep Quality Index (PSQI), timing of sleep (Morningness-Eveningness Questionnaire [MEQ]), self-esteem (Rosenberg Self-Esteem Scale) and physical activity (International Physical Activity Questionnaire) assessments
- Blood for future research collected (30 ml)
- Coaching about the two diet options
- Installation of LoseIt! application on smartphone
- Determination of baseline energy requirement (*see below*)
- Randomization group assigned (participant blinded)
- Stool sample kit collection

At follow-up visits (months 3 and 6), the following will be done:

- Vital signs and waist circumference
- Patient-Determined Disease Steps (month 6 only)
- Health-related quality of life (Functional Assessment in MS [FAMS]), fatigue (PROMIS fatigue), Pittsburgh Sleep Quality Index (PSQI), timing of sleep (Morningness-Eveningness Questionnaire [MEQ]), self-esteem (Rosenberg Self-Esteem Scale) and physical activity (International Physical Activity Questionnaire) assessments
- Blood for future research (30 ml/visit)
- Stool sample kit distribution (at month 3) and collection (at month 6)
- Collection of LoseIt! application data (calorie counts) since prior visit

Determination of Baseline Energy Requirement and Diet Details: The baseline energy requirement (total energy expenditure) of each participant will be determined prior to randomization. This measurement is defined as the number of calories needed to maintain the current body weight. Total energy expenditure will be assessed using validated equations from University of Arizona Calorie Need Estimates, which include an individual's estimated resting

Date: 7/20/16

Principal Investigator: [name], MCR

Application Number: IRB00095554

energy expenditure (based on current weight, height and age) and physical activity (based on the International Physical Activity Questionnaire short form).

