Age 18-75 years; meets 2010 criteria for MS	To ensure broadly generalizable to the MS patient population
Body mass index (BMI) < 25 kg/m ² , or if higher, participant was unwilling to enroll in calorie restriction study	Only want to enroll overweight or obese individuals if they are unwilling to restrict calories, as calorie timing study unlikely to lead to weight loss
No history of diabetes requiring medication	To avoid unpredictable hypoglycemia
Not pregnant, willing to avoid becoming pregnant during the study, and not breastfeeding	To avoid danger to fetus or threats to milk supply or health
No history of an eating disorder	To prevent relapse of eating disorder
No current use of warfarin	To avoid INR fluctuations
No history of major surgery within past 3 months	To prevent improper wound healing
Have a smart phone with the capability of taking and storing photographs	To provides study team with time stamps indicating timing of oral intake.

4. Drugs/ Substances/ Devices

- a. The rationale for choosing the drug and dose or for choosing the device to be used. N/A
- b. Justification and safety information if FDA approved drugs will be administered for non-FDA approved indications or if doses or routes of administration or participant populations are changed. N/A
- c. Justification and safety information if non-FDA approved drugs without an IND will be administered. N/A

5. Study Statistics

a. Primary outcome variable.

Calorie restriction study: Change in waist circumference

Calorie timing study: Change in metabolism biomarkers

b. Secondary outcome variables.

Calorie restriction study: Change in body mass index, number of pounds lost, percentage adherence to recommended calorie intake, changes in health-related quality of life, changes in fatigue and sleep

Calorie timing study: Adherence to photographing foods, changes in health-related quality of life, fatigue, and sleep

c. Statistical plan including sample size justification and interim data analysis.

Summary statistics (mean \pm standard deviation, median and interquartile range, or number and percentages) will be used to describe the outcomes.

Calorie Restriction:

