For the primary objective, the impact of increased patient engagement via the smartphone on weight loss (pounds lost, change in body mass index, and change in waist circumference) as well as on the percentage adherence to the recommended calorie intake (as assessed by LoseIt! logs) will be evaluated in t-tests. If there are baseline imbalances in potentially meaningful covariates despite randomization, multivariate approaches accounting for imbalanced covariates will be employed.

For the secondary objective, the primary analysis will evaluate the association of weight loss (change in body mass index as well as change in waist circumference) with changes in health-related quality of life, sleep and fatigue using multivariate linear regression adjusted for age, sex, race, change in physical activity and baseline disability. Whether group assignment (extra smartphone engagement or standard of care) influences this relationship will also be evaluated.

The rationale for measuring change in waist circumference as the primary outcome is that waist circumference, rather than body mass index, is considered a better measure of the risk of metabolic syndrome.²⁰ However, for comparability with previously-published studies and in order to further evaluate the relationship between waist circumference with body mass index, both measures will be obtained.

Calorie Timing:

Metabolomics will be conducted on samples from the participants to evaluate the impact of restricting the hours in which foods are consumed. Primary analyses will be intent-to treat; secondary analyses will investigate with the actual time of day metrics, as assessed by time stamps of smartphone photos, are predictive of changes in metabolism. Secondary outcomes will be assessed as above.

d. Early stopping rules.

Participants who become pregnant, experience weight loss with BMI < 20 kg/m², or who develop another issue that, in the estimation of the investigator, puts them at risk of ongoing participation, the participant will be asked to cease following the diet but will be followed to the completion of the study.

6. Risks

a. Medical risks, listing all procedures, their major and minor risks and expected frequency.

- Calorie-restriction diet
 - The risks associated with the diets are not known
 - Previous studies of similar diets in humans have not shown any serious risks.
 -

-
- Calorie timing diet
 - Participants may be hungrier in the time in which foods are not being consumed

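### Waist circumference is read twice before randomisation in the calorie restriction study, but the plan gives the consent reading no analytic role and tests change in waist by unadjusted t-tests

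*Combined protocol and SAP*

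**What the plan says.** Section 2a (calorie restriction study, schedule of events) has two visits before treatment starts: "Patients will be consented one month prior to the baseline visit". At the first, "At the consent visit, baseline energy requirement will be determined (see below) and the patient's waist circumference will be measured", and a standard tape procedure is described. The baseline-visit list opens with "Vital signs and waist circumference" and reaches group assignment near its end, so both waist readings precede randomisation. The one stated use of the earlier reading is a trigger: if waist differs by 10% or more "from the consent visit, baseline energy requirement will be re-calculated".

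Section 5a gives the primary outcome as "Calorie restriction study: Change in waist circumference". Section 5c says that the weight-loss measures ("pounds lost, change in body mass index, and change in waist circumference") and calorie adherence "will be evaluated in t-tests". Multivariate adjustment follows only if potentially meaningful covariates turn out imbalanced. Section 5 does not mention the consent reading, does not name baseline waist as a covariate, and does not say which reading is the start value for change.

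**The concern.** A single tape reading carries measurement error, and a change score takes in that error in full from both ends. A second reading taken before randomisation gives further information on each participant's true starting waist. If it goes unused, the primary comparison may be less precise than the data allow. That matters in a study of 80 drawn from a small pool: two-thirds of 140 infusion patients is about 93, so recruiting more people is not an easy way to gain precision.

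The plan's silence is a weakness in itself. Two readings could each serve as baseline, and no rule fixed in advance says how either enters the analysis.

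**Working it through.** **No figure in the plan to reproduce.** The calorie restriction sample size of 80 comes without alpha, power, effect size, SD or dropout. The documents also give no SD, correlation or measurement error for waist. Everything below rests on assumed values.

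**Assumptions.** Between-person SD B = 14 cm; SD of true change from the baseline visit to follow-up d = 5 cm; SD of error in a single reading e = 1 to 5 cm; SD of true drift from consent to baseline w = 0 or 1.5 cm. Errors are independent.

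**Formulas.** The residual variance of follow-up waist is d² + e² plus the remaining uncertainty about true waist at the baseline visit.

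- Baseline-visit reading only: d² + e² + (B² + w²)e² / (B² + w² + e²).
- Both readings as covariates: d² + e² + Pe² / (P + e²), where P = w² + B²e² / (B² + e²).

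**Example (e = 2, w = 0).** One reading: 25 + 4 + 196×4/200 = 32.92. Both: P = 3.92, so 29 + 3.92×4/7.92 = 30.98. The fall is 1 − 30.98/32.92 = 5.9%.

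| e (cm) | One, w = 0 | Both, w = 0 | Fall | One, w = 1.5 | Both, w = 1.5 | Fall |
|---|---|---|---|---|---|---|
| 1 | 26.99 | 26.50 | 1.8% | 26.99 | 26.76 | 0.9% |
| 2 | 32.92 | 30.98 | 5.9% | 32.92 | 31.43 | 4.5% |
| 3 | 42.60 | 38.40 | 9.9% | 42.61 | 38.92 | 8.7% |
| 4 | 55.79 | 48.69 | 12.7% | 55.81 | 49.25 | 11.7% |
| 5 | 72.17 | 61.75 | 14.4% | 72.20 | 62.35 | 13.6% |

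**Cost of the extra covariate.** With 80 participants, residual degrees of freedom go from 77 to 76, and 77/76 = 1.013. A cost of roughly 1.3% offsets most of the 1.8% gain at e = 1 without drift, and all of the 0.9% gain with drift.

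**Compared with the planned t-test.** The variance of change from the baseline visit is d² + 2e², which is 27 at e = 1 and 75 at e = 5. Adjusting for one reading gives 26.99/27 = 1.00 to 72.17/75 = 0.96 of that. Under this model most of the gain therefore comes from the second reading.

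**Why not the mean.** Change from the mean of the two readings has variance d² + w²/4 + 1.5e². This exceeds d² + 2e² once w is above 1.41e.

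- At d = 5, e = 1, w = 1.5 it is 27.06 against 27, slightly worse.
- At d = 2, e = 1, w = 2 it is 6.5 against 6, about 8% worse.

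Two separate covariates let the data weight the readings, so residual variance does not rise.

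**A case with no gain.** If waist followed a first-order autoregressive process (monthly correlation 0.97 to 0.99), the consent reading would add nothing to the baseline-visit reading: the variance ratio is 1.00 with two covariates and 1.03 to 1.04 with averaging.

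**The case against.** The strongest reply is that this is a refinement. Using the randomisation visit as baseline is conventional and unbiased, this is a pragmatic pilot, and the consent reading has a purpose of its own. The gain may also be close to nil. The tape procedure is standardised, so an error near 1 cm cannot be ruled out. The upper end fits poorly with the 10% trigger: on an assumed waist of 100 cm, error alone would set it off with probability 2[1 − Φ(10/(e√2))], which is 16% at e = 5, 8% at e = 4 and 0.04% at e = 2. All of this stands, and it limits the size of the point. It does not remove it, because the readings are already collected and the change is small.

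Four stronger readings are tempting, and the documents do not support them.

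- A reader might infer that the consent reading is discarded. The plan never says so: the start value for change is undefined, and the reading is neither included nor excluded.
- A reader might take the mean of the two readings to be an equal remedy. It can lose precision if waist drifts in a month when participants have already agreed to a weight-loss study.
- A reader might apply averaging to Secondary Objective A, where change in waist is the exposure. Quality of life, fatigue and sleep are first listed at the baseline visit, so the waist window would open up to a month before theirs.
- A reader might extend the point to weight and BMI. The energy equations use current weight, but section 2a lists no weight measurement at the consent visit, and vital signs appear only from baseline.

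**Conclusion.** The point holds as a low-cost improvement to the primary analysis of the calorie restriction study. Two pre-randomisation waist readings exist, the plan gives the first no analytic role, and the planned test is unadjusted. Entering both as covariates lowers residual variance by about 2% to 14% relative to one baseline reading, or about 1% to 14% with a drift SD of 1.5 cm, under the assumed values (B = 14 cm, d = 5 cm, e = 1 to 5 cm). At the bottom of that range the lost degree of freedom cancels much or all of the gain; apart from that, precision is not lost. The comparison stays unbiased because both readings precede allocation.

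These are patient-level figures. Section 2a describes randomisation as stratified by week, while section 2c describes it as clustered by week. If it is clustered, the percentages should not be turned into equivalent sample sizes. The missing sample size justification and the undefined primary time point may matter more for precision than this point does.

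**What to change.** In 5c, replace the t-test for the primary waist comparison with a linear model (ANCOVA) of waist at a named follow-up visit, or of its change from the baseline visit, on group, with baseline-visit waist and consent-visit waist as two separate covariates. The group estimate is the same for either outcome, because baseline-visit waist is in the model. If the consent reading is missing, use the baseline-visit value alone so that the participant stays in the analysis.

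Do not define baseline as the mean of the two readings. For Secondary Objective A, state that waist change starts from the baseline visit, to match the questionnaires. Leave weight and BMI out of this change.

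The cost is a sentence or two in 5c and one degree of freedom for the second reading. No new measurement is needed.

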Participants will receive education about two diet approaches: intermittent calorie restriction and continuous calorie restriction. For the intermittent calorie restriction group, a standardized percentage reduction to 25% of the baseline energy requirement will be used two days a week. For the continuous calorie restriction group, the same percentage calorie reduction will be provided, but the restriction will take place over an entire seven-day period (i.e. the group will be provided with food containing 78.6% of their baseline energy requirement (calories) each day. All participants will be encouraged to drink water liberally to stave off hunger. If a participant in one group is unable to follow their chosen diet, rather than losing the subject as a drop-out, the subject will switch to other dietary approach.

Adherence Intervention: All subjects will be asked to document adherence using the LoseIt! application, which tracks calorie intake based on food items and quantity consumed. The application will be installed on the subjects' smartphones at the baseline visit, and they will be instructed how to use it.

Subjects will be randomized 1:1, stratified by week of enrollment, to receive electronic adherence support or to the standard of care (no additional contact). The stratified randomization was chosen because participants often receive their infusions at the same time due to the 28-day dosing schedule, and thus may otherwise discuss their impressions of the study with other participants who happen to be infused at the same time. Those who are in the intervention arm will be sent a text message once a week providing encouraging information about the health benefits of weight loss and, where possible, specifically focusing on how it may benefit their MS. They will be asked to send the previous week's log of calories consumed to the research group (this information is readily available using the LoseIt! application).

Calorie Timing Study

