- Health-related quality of life (Functional Assessment in MS [FAMS]), fatigue (PROMIS fatigue), Pittsburgh Sleep Quality Index (PSQI), and physical activity (International Physical Activity Questionnaire) assessments
- Blood for future research
- Stool sample kit distribution (at month 3) and collection (at month 6)
- Collection of photographic data since prior visit

b. Study duration and number of study visits required of research participants.

The study duration is 6 months from the baseline visit. Follow-up visits will be done at the patients' scheduled infusion appointments at months 3 and 6.

c. Blinding, including justification for blinding or not blinding the trial, if applicable.

Subjects will be blinded to the study hypothesis that additional electronic support will help improve dietary adherence, which could influence and confound the results. Subjects will be told that the study is evaluating how easily changing calorie amounts or timing can be done in the real world and that, in addition to the baseline education, they may receive periodic contact from the study team via text message. For the calorie restriction study, both groups will receive reminder text messages about the month 3 and 6 study visits, which will help prevent unblinding. Further, the randomization strategy employed (clustered by week of baseline visit) will prevent contamination of patients who may discuss the study while getting infused, since the infusions are scheduled on an every 28-day basis and thus participants would co-mingle in the infusion center and may discuss their experience of the study. For the calorie timing study, participants will be sent text messages in the morning twice a week instructing them to capture

all foods and beverages they consume in the next 24 hours on their smartphone and to save those photos.

d. Justification of why participants will not receive routine care or will have current therapy stopped.

This study does not require any changes to the participants' medical therapies, and they will continue to receive routine care.

e. Justification for inclusion of a placebo or non-treatment group.

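### Nothing in the plan keeps staff who know the arm from taking the month 3 and 6 waist readings, the primary outcome of the calorie restriction study

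*Combined protocol and SAP*

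**What the plan says.** Section 5a names the primary outcome: "Calorie restriction study: Change in waist circumference". Section 2a, Study Procedures/Schedule of Events, describes the measurement: "Waist circumference will be measured according to NIH protocol". It goes on to give stance, arm position, muscle relaxation, the iliac-crest landmark and the phase of breathing. The overview in 2a sets the timing after randomization: "At the routinely-scheduled infusions at months 3 and 6, body mass index, waist circumference, and fatigue/HRQoL/self-esteem will be evaluated". None of these places names the measurer.

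On blinding, section 2c says: "Subjects will be blinded to the study hypothesis that additional electronic support will help improve dietary adherence". The baseline visit list in 2a likewise marks the assignment as blinded to the participant. No statement concerns the staff who assess outcomes.

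On contact with the arms, the Adherence Intervention paragraph of 2a says: "Those who are in the intervention arm will be sent a text message once a week". The same participants are asked to send the previous week's "log of calories consumed to the research group". The comparator gets no additional contact, apart from the visit reminders that 2c gives to both arms.

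**The concern.** A tape reading leaves some judgement to the person taking it: exact placement, tension, and the moment of reading. If that person knows the arm and the hypothesis, a small average difference in how the two arms are measured passes straight into the between-arm comparison of the primary outcome. Adjusting for baseline covariates, which section 5c allows, cannot remove it.

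In this design knowledge of the arm is easy to come by. Whoever handles the weekly logs knows that a participant who sends them is in the intervention arm. The plan does not separate that task from measuring waist at months 3 and 6. Section 2c is where one would expect either masking of the assessor or a reason for doing without it, and it gives neither.

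**Working it through.** **1. Can the arm reach the measurer?** Three parts of the plan bear on this.

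- *Allocation* (2a, Enrollment and Randomization): made by the study statistician. Nothing is said about who else sees it.
- *Weekly messages and logs* (2a, Adherence Intervention; Primary Objective): they run between the intervention arm and the research group. Sharing with the team is part of the intervention itself.
- *Month 3 and 6 visits* (2a): waist is on the same list as vital signs and the collection of LoseIt! data. The LoseIt! data come from everyone, so collecting them at the visit does not reveal the arm. The weekly submission does.

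The plan therefore permits a measurer who knows the arm, but does not establish that there will be one.

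**2. How much could it matter?** The plan states no alpha, power, effect size or SD for this study, so there is no figure of its own to reproduce. What follows is an illustration.

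Inputs from the documents: 80 patients (2a, Overview) randomized 1:1, hence 40 per arm, compared by t-test (5c).

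Assumed inputs: individual randomization, no dropout, two-sided alpha of 5%, no true effect, SD of waist change of 4, 6 or 8 cm, and a between-arm measuring bias b of 0.5 or 1 cm.

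Formulas (normal approximation):

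- SE = SD × √(2/40), which gives 0.89, 1.34 and 1.79 cm for SD 4, 6 and 8.
- Rejection probability = Φ(b/SE − 1.96) + Φ(−b/SE − 1.96).

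Worked case, SD 6 and b = 1: b/SE = 1/1.342 = 0.745. Then Φ(−1.215) + Φ(−2.705) = 0.112 + 0.003, or 11.6% before rounding of the parts.

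| SD of change | b = 0 | b = 0.5 cm | b = 1 cm |
|---|---|---|---|
| 4 cm | 5% | 8.6% | 20.1% |
| 6 cm | 5% | 6.6% | 11.6% |
| 8 cm | 5% | 5.9% | 8.6% |

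A noncentral t with 78 degrees of freedom gives 11.4% at SD 6 and b = 1, so the approximation is adequate. At that point 11.2 of the 11.6 percentage points lie in the direction that the bias favours, against 2.5 with no bias.

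For scale, the difference detectable with 80% power at SD 6 is (1.96 + 0.84) × 1.342 ≈ 3.8 cm. A 1 cm bias is a little over a quarter of that.

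**The case against.** The strongest reply is that silence is not exposure. The visits are routine infusion appointments and waist is listed with vital signs, so the tape may already be held by infusion staff who never see a log. In that case the fix only writes down existing practice. This stands as a limit on the claim: a reader might infer that unmasked staff will measure, and the documents do not support that. They do not rule it out either, and one sentence would.

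The NIH procedure narrows the measurer's discretion. It does so mainly for random error, and does not prevent a consistent lean by someone who knows the arm. Pounds lost and change in body mass index are tested alongside waist, so an isolated waist artefact might look discordant. That is a useful check, but it does not protect the outcome named as primary.

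This is a pragmatic pilot with no stated alpha or power, so false-positive rates should be read as a measure of scale and not as the failure of a confirmatory test. That is fair. Masking the measurer would still leave delivery of the intervention unchanged.

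Two stronger readings are tempting.

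- **The visit week reveals the arm.** Section 2c describes randomization as clustered by week of baseline visit, and under that wording it could. The Adherence Intervention paragraph in 2a instead describes 1:1 randomization stratified by week, under which it does not. The calculation above also assumes individual randomization and would not apply under clustering.
- **A 2 cm bias.** The same formula then gives about 20% to 61%. Nothing in the documents supports so large a shift, which exceeds half the 3.8 cm detectable difference at SD 6.

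**Conclusion.** The point holds as a gap in protection. The primary outcome depends on an assessor, blinding is stated for participants only, one arm alone sends weekly logs to the research group, and nothing keeps those staff from measuring after randomization. It does not show that bias will occur.

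On the stated assumptions the effect is modest at 0.5 cm (about 6-9% false positives in place of 5%) and appreciable at 1 cm (about 9-20%). Only the sample size, the allocation ratio and the use of a t-test come from the documents. The conclusion about missing protection does not depend on the illustration. The change is worth making because it is cheap and acts on a direct source of bias in the primary comparison.

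**What to change.** State in 2a and 2c that waist and weight at months 3 and 6 are taken by existing visit staff, for example those who take vital signs, who have no access to the allocation list, the messages or the weekly logs. State also that they do not see the earlier waist readings at those two visits.

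Baseline needs no change provided waist is measured before the arm is assigned; the plan should say so. The comparison of baseline with consent-visit waist, which triggers recalculation of the energy requirement at a difference of 10% or more, stays as it is. Averaging repeat readings is not a substitute, since it reduces random error and not bias from knowing the arm.

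The cost is reassigning a task and training those staff in the tape procedure. No additional assessor or visit is needed. Masking will be imperfect because participants may mention the messages. The leak would be larger if allocation is by week, since one remark could then identify everyone seen that week. The stratified and clustered descriptions in 2a and 2c must be reconciled as a separate matter.

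### Sections 2a and 2c name different units of randomisation for the calorie restriction study: the planned t-tests suit patients stratified by week, and the contamination rationale suits whole weeks as clusters

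*Combined protocol and SAP*

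**What the plan says.** Four places in the protocol bear on how the calorie restriction study is randomised and analysed.

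- Section 2a, Enrollment and Randomization: participants are randomised 1:1 by the study statistician. No strata, blocks or clusters are named.
- Section 2a, Adherence Intervention: "Subjects will be randomized 1:1, stratified by week of enrollment, to receive electronic adherence support" or standard of care. The reason given is that, on the 28-day infusion schedule, participants "may otherwise discuss their impressions of the study with other participants who happen to be infused at the same time".
- Section 2c, Blinding: "the randomization strategy employed (clustered by week of baseline visit) will prevent contamination of patients who may discuss the study while getting infused". The same section relies on participants not knowing what is being tested: "Subjects will be blinded to the study hypothesis that additional electronic support will help improve dietary adherence".
- Section 5c, Calorie Restriction: the effects of the messaging on pounds lost, body mass index, waist circumference (the primary outcome in 5a) and percentage adherence, the last "as assessed by LoseIt! logs) will be evaluated in t-tests". The only other provision for this comparison is: "If there are baseline imbalances in potentially meaningful covariates despite randomization, multivariate approaches accounting for imbalanced covariates will be employed". There is no week term, cluster level, ICC or number of weeks.

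The two sections also define the week differently. Section 2a uses enrollment, which is not defined, and 2c uses the baseline visit. The schedule of events puts consent one month before baseline and assigns the group at baseline.

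**The concern.** Stratifying by week and clustering by week are opposite designs. With strata, patients are randomised within a week and the aim is to have both arms in it. With clusters, everyone in a week receives the same arm. The two sections give the same purpose, keeping patients who share the infusion room from comparing experiences, yet they describe schemes that do opposite things to that risk.

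The unit of randomisation decides how the allocation list is built, whether the protection claimed in 2c exists, and whether a test that treats patients as independent is valid. A list drawn up now would contradict one of the two sections, and a wrong allocation cannot be undone after enrolment.

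**Working it through.** **Each reading set against the rest of the plan**

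| | Weeks are strata | Weeks are clusters |
|---|---|---|
| Unit | Patient | Week |
| Arms present in one week | Both | One |
| Contamination rationale (2a) | Not served: arms share the infusion room | Served |
| Prevention claim (2c) | False | Plausible, subject to the 28-day point below |
| Patient-level t-tests (5c) | Valid | Ignore the unit of allocation |

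The covariate provision in 5c does not rescue the cluster reading. Each week then holds one arm, so week as a fixed covariate is aliased with arm.

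**Inputs.** From the documents: 80 patients (2a, Overview) and a 28-day cycle. The figure of 80 cannot be reproduced, because 5c gives no alpha, power, effect size or standard deviation. Assumed: all 80 analysed, k equal weeks of m = 80/k patients, half the patients per arm, total variance 1, two-sided 5%, ICC from 0 to 0.05.

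**If weeks are clusters and the t-test ignores them**

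- Design effect DE = 1 + (m − 1) × ICC; effective N = 80/DE.
- True variance of the arm difference = (4/80) × DE.
- Pooled sum of squares SS = (1 − ICC) χ²(80 − k) + DE χ²(k − 2).
- Type I error = average over SS of P(|Z| > t(0.975, 78) × √(SS/78/DE)).

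Example, k = 4 and ICC 0.05: DE = 1 + 19 × 0.05 = 1.95 and effective N = 80/1.95 = 41.

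A valid test on cluster means has interval half-width t(0.975, k − 2) × √(0.05 × DE). For independent patients it is t(0.975, 78) × √0.05 = 0.445. For k = 4 and ICC 0.05 it is 1.344, and 1.344/0.445 = 3.02.

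| Weeks (patients per week) | Type I error %, ICC 0 / 0.01 / 0.02 / 0.05 | Effective N at ICC 0.05 | Width of valid interval relative to 0.445, ICC 0 to 0.05 |
|---|---|---|---|
| 4 (20) | 5.0 / 7.3 / 9.6 / 16.3 | 41 | 2.16 to 3.02 |
| 8 (10) | 5.0 / 6.1 / 7.1 / 10.4 | 55 | 1.23 to 1.48 |
| 16 (5) | 5.0 / 5.5 / 5.9 / 7.4 | 67 | 1.08 to 1.18 |
| 20 (4) | 5.0 / 5.4 / 5.7 / 6.8 | 70 | 1.06 to 1.13 |

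A patient-level simulation agreed with the type I errors within Monte Carlo error, and the cluster-mean test held 4.9% to 5.2% throughout.

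**If weeks are strata, balanced within week, and the t-test ignores them.** Week effects cancel from the difference, whose variance is (4/80) × (1 − ICC). The pooled SS still carries them: (1 − ICC) χ²(79 − k) + (1 − ICC + m × ICC) χ²(k − 1). Type I error runs from 5.0% at ICC 0 down to about 4.5% at ICC 0.05. Fitting week changes the interval width by between 2.1% narrower and 0.5% wider.

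**The 28-day cycle.** Patients whose baseline visits fall four weeks apart are infused in the same week from then on. To keep arms apart at every infusion, all weeks in the same cycle position must share an arm. That leaves at most 28/7 = 4 groups.

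**The case against.** A reader might infer that 2a simply misnames an intended cluster scheme. The contamination rationale does point that way. The operative wording does not: both randomisation statements in 2a speak of participants or subjects randomised 1:1, 2a uses the word stratified twice, and the group is assigned at each participant's baseline visit. Clustering appears once, in a parenthesis in the blinding section. The documents leave the unit open.

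A reader might also infer that the t-tests are wrong outright, or that the trial carries a 16% type I error. Neither is supported. Under stratification the t-tests are valid and slightly conservative. Section 5c does not state the unit of the t-tests, so patient-level is the natural reading but still an inference. The 16% figure needs four clusters and an ICC of 0.05 together; with 16 to 20 weeks and an ICC of 0.01 to 0.02, the error is 5.4% to 5.9%.

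Finally, this is a pilot with no stated alpha, power or confirmatory claim, which lessens the weight of a modest inflation. It does not excuse an undefined unit of randomisation, since the plan still tests between arms for its primary objective. It is also true that a patient-level list could be drawn up from 2a alone, but that list would contradict 2c.

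**Conclusion.** The point stands as an unresolved contradiction in the unit of randomisation, in current text. That much is certain and rests on no assumption, and it is enough to require correction before allocation.

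The analysis defect is conditional. It exists only if weeks are clusters, the t-tests are patient-level and the ICC is above zero. Its size then ranges from negligible (many small weeks, low ICC) to serious (four weeks, ICC 0.05), and the documents do not allow the range to be narrowed. If weeks are strata, the analysis is sound, and it is the contamination rationale and the prevention claim that are wrong.

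**What to change.** State one unit of randomisation and one definition of week in 2a and 2c, and make 5c match. The choice belongs to the sponsor.

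(a) If weeks are clusters: state how many weeks there are and how they are allocated to arms. Replace the t-tests with a test on cluster means (degrees of freedom = clusters minus 2), or with a mixed model with a random week effect and small-sample degrees of freedom if there are enough weeks. Report the reduced effective sample size. Unless allocation is by position in the 28-day cycle, soften the claim in 2c that contamination is prevented. The cost is precision: intervals about 6% to 18% wider with 16 to 20 weeks, and 2.2 to 3.0 times as wide with four. With four groups split 2:2 there are only 6 possible allocations, so the smallest two-sided re-randomisation p-value is 2/6 = 0.33.

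(b) If weeks are strata: keep the t-test; fitting week is optional, with little to gain. Remove the contamination rationale from 2a and the prevention claim from 2c, and list contamination and weaker blinding to the hypothesis as limitations. The cost is a protection that the protocol claims twice. The direction of any resulting bias cannot be established from the documents.

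Either way the change is wording in 2a, 2c and 5c, plus one model statement under (a). No new measurements are needed.
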